## 6.3.4.9 Pain Relapse from 2 to 48 Hours Post-Dose

Pain relapse from 2 to 48 hours post-dose is defined as pain of mild, moderate, or severe at any time point post-dose after 2 hours post-dose for subjects with pain level of none at 2 hours post-dose. Thus, analyses of pain relapse will be based on mITT subjects with pain freedom at 2 hours post-dose (see Section 6.3.3.1).

Subjects who meet all of the following criteria will be classified as non-relapsers:

- Pain level of none at all time points after 2 hours post-dose, i.e., in the 3 to 48-hour post-dose analysis windows
- Missing data at  $\leq 1$  time point after 2 hours post-dose, i.e., in the 3, 4, 6, 8, 24, or 48-hour post-dose analysis window
- No intervening rescue medication taken at or before 48 hours post-dose (see Section 6.3.4.6).

Otherwise, subjects who are not classified as non-relapsers and have any of the following will be classified as relapsers:

- Intercurrent event: Rescue medication taken at or before 48 hours post-dose (RM=F; see Section 6.3.4.6)
- Mild, moderate or severe pain at any time point after 2 hours post-dose, i.e., in the 3, 4, 6, 8, 24, or 48-hour post-dose analysis window
- Missing pain level at > 1 time point after 2 hours post-dose (NC1=F), i.e., in the 3, 4, 6, 8, 24, or 48-hour post-dose analysis window.

Pain relapse from 2 to 48 hours outcomes will be summarized by treatment group as the number and percentage of subjects in the following categories:

- Non-relapser: no pain at all time points after 2 hours post-dose, missing data at ≤ 1 time point after 2 hours post-dose, and no intervening rescue medication taken at or before 48 hours post-dose
- Relapser
  - o Rescue medication taken at or before 48 hours post-dose (RM=F)
  - o Mild, moderate or severe pain at any time point after 2 hours post-dose
    - Severe pain
    - Moderate pain
    - Mild pain
  - $\circ$  Missing pain level at > 1 time point after 2 hours post-dose (NC1=F).

Relapser subcategories are mutually exclusive, because subjects who meet more than 1 relapse criterion will be classified according to the first relapse criterion met; in case of ties, the first relapse subcategory that is met in the hierarchy above will be chosen.

Treatment group comparisons of the percentage of subjects with pain relapse from 2 to 48 hours post-dose will use analogous methods as the principal analysis of the co-primary endpoint of pain freedom with NC1=F and RM=F (see Section 6.3.3.1).

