- 12. Sustained pain relief from 2 to 48 hours, will be assessed using the number of subjects that do not experience any moderate or severe migraine pain through the time period of interest.
- 13. Sustained pain freedom, from 2 to 48 hours, will be assessed using the number of subjects that do not experience any migraine pain through the time period of interest.
- 14. Freedom from Nausea will be assessed by tabulating the number of subjects that report the absence of nausea at 2 hours post-dose in the subset of subjects that reported the presence of nausea at migraine baseline.
- 15. Pain relapse will be assessed using the number of subjects that are pain free at 2 hours post-dose and then have migraine pain of any severity (response of 1, 2 or 3 on the 4 point scale) within 48 hours after administration of study medication.

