# 1.2.2 Secondary Objectives

The secondary objectives are:

- To evaluate BHV-3500 compared to placebo on pain relief at 2 hours post-dose.
- To evaluate the effect of BHV-3500 relative to placebo on the patient's ability to function normally at 2 hours post-dose according to the Functional Disability scale.
- To evaluate BHV-3500 compared to placebo on the probability of requiring rescue medication within 24 hours of initial treatment.
- To evaluate BHV-3500 compared to placebo on freedom from photophobia at 2 hours postdose.
- To evaluate BHV-3500 compared to placebo on freedom from phonophobia at 2 hours post-dose.
- To evaluate BHV-3500 compared to placebo on pain relief at 60 minutes post-dose.
- To evaluate the effect of BHV-3500 relative to placebo on the patient's ability to function normally at 60 minutes post-dose according to the Functional Disability scale.
- To evaluate BHV-3500 compared to placebo on pain relief at 30 minutes post-dose.
- To evaluate the effect of BHV-3500 relative to placebo on the patient's ability to function normally at 30 minutes post-dose according to the Functional Disability scale.

- To evaluate BHV-3500 compared to placebo on sustained pain relief from 2 to 24 hours post-dose.
- To evaluate BHV-3500 compared to placebo on sustained pain freedom from 2 to 24 hours post-dose.
- To evaluate BHV-3500 compared to placebo on sustained pain relief from 2 to 48 hours post-dose.
- To evaluate BHV-3500 compared to placebo on sustained pain freedom from 2 to 48 hours post-dose.
- To evaluate BHV-3500 compared to placebo on freedom from nausea at 2 hours post-dose.
- To evaluate BHV-3500 compared to placebo for the incidence of pain relapse from 2 to 48 hours post-dose.

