	nausea present at on-study migraine attack onset
Objective	Pain Relapse from 2 to 48 hours post-dose
	Percentage of subjects with (1) mild, moderate, or severe pain at any time point after
Endpoint	2 hours post-dose (2) missing pain data at $\leq 1$ time point after 2 hours post-dose, and
	(3) no intervening rescue medication taken at or before 48 hours post-dose;
	evaluated for subjects with pain freedom at 2 hours post-dose

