# 6.1.2 Type I Error Control

Type I error will be controlled by a hierarchical gate-keeping procedure. First, the family of two co-primary endpoints will be tested. In particular, each BHV-3500 treatment group will be tested for superiority against placebo at a Bonferroni corrected alpha=0.0167 level for both co-primary endpoints. If both co-primary endpoint tests are determined to be significant for a BHV-3500 treatment group versus placebo, then the secondary endpoints will be tested for that BHV-3500 treatment group versus placebo using a hierarchical gate-keeping procedure, with each test in the hierarchy conducted at alpha=0.0167.

The secondary endpoints will be tested in the order shown in Section 1.2.2.

If a test in the hierarchy is not significant, then any further tests on endpoints in the sequence will have p-values presented only for descriptive purposes, and no conclusions will be drawn from those results.

For exploratory endpoints, no attempt will be made to adjust for multiplicity. Any exploratory endpoints for which p-values are produced will be evaluated at an unadjusted two-sided alpha level of 0.05 and presented only for descriptive purposes.

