### 6.3.4.10 Overall Summary of Primary and Secondary Endpoints

An overall summary of treatment comparisons of all primary and secondary endpoints tested hierarchically will present the following statistics:

- Overall response rate (i.e., "n/N" and percentage) and 98.3% CI for each treatment group
- Stratified percentage difference between treatment groups (BHV-3500 placebo), 98.3% CI, and p-value.

Analyses will be based on principal methods described in Sections 6.3.3 and 6.3.4. Endpoints will be displayed in the order presented in Sections 1.2.1 and 1.2.2. P-values that are determined to be significant based on the testing hierarchy will be flagged.

A forest plot of treatment comparisons of all primary and secondary endpoints tested hierarchically will be produced for each treatment group comparison of BHV-3500 versus placebo based on the overall summary. Each plot will display the following statistics:

- Overall response rate (i.e., "n/N" and percentage) for the BHV-3500 treatment group and placebo
- Stratified percentage difference between treatment groups (BHV-3500 placebo) and 98.3% CI.

Percentage differences with p-values that are determined to be significant based on the testing hierarchy will be flagged. Note that each plot will display results for *no* intervening rescue medication use within 24 hours post-dose and *no* pain relapse from 2 to 48 hours post-dose so that positive percentage differences will favor BHV-3500 for these secondary endpoints.

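### Pain relapse, the last test in the hierarchy, is compared only among subjects pain free at 2 hours, so a significant difference cannot be attributed to a drug effect on relapse

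*SAP*

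**What the plan says.** The fifteenth and last secondary objective in SAP 1.2.2 is: "To evaluate BHV-3500 compared to placebo for the incidence of pain relapse from 2 to 48 hours post-dose". Protocol 3.2 item 15 defines the count but no denominator: "Pain relapse will be assessed using the number of subjects that are pain free at 2 hours post-dose and then have migraine pain". The SAP supplies the denominator. Table 2 says "evaluated for subjects with pain freedom at 2 hours post-dose", and 6.3.4.9 says: "Thus, analyses of pain relapse will be based on mITT subjects with pain freedom at 2 hours post-dose".

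The comparison is inferential: "Treatment group comparisons of the percentage of subjects with pain relapse from 2 to 48 hours post-dose will use analogous methods as the principal analysis". That means the stratified Cochran-Mantel-Haenszel comparison used for pain freedom, at alpha 0.0167. SAP 6.1.2 states "Type I error will be controlled by a hierarchical gate-keeping procedure" and "The secondary endpoints will be tested in the order shown in Section 1.2.2", so relapse is the final step of that procedure. SAP 6.3.4.10 flags hierarchically significant results and plots the absence of relapse "so that positive percentage differences will favor BHV-3500 for these secondary endpoints". Neither document gives a principal-stratum estimand, an adjustment, a sensitivity analysis or a caveat for this comparison.

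**The concern.** Being pain free at 2 hours is an outcome the drug is meant to change. If the drug works, the active subset holds two kinds of subject: those who would have been pain free on placebo too, and those pain free only because of the drug. The placebo subset holds only the first kind. If the two kinds differ in their tendency to relapse, the arms will differ in relapse even when the drug alters nobody's relapse risk.

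The order of testing does not remove this. A dose reaches the relapse test only after it is superior on 2-hour pain freedom, which is when the subsets are expected to differ in make-up. The other subset endpoints (normal function, photophobia, phonophobia, nausea) condition on status at attack onset, before dosing, and do not share the problem. At stake is one claim: a flagged result on relapse, shown beside the other confirmatory results and open to being read as a treatment effect.

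**Working it through.** **Inputs from the documents.** Protocol 9.2 and SAP 5: about 380 mITT subjects per arm; 2-hour pain freedom 22% v 12%; MBS freedom 45% v 32%; alpha 0.0167. SAP 6.3: confidence intervals are two-sided.

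**The plan's own figure first.** Power = Φ[(d − z·SE0)/SE1], with z = 2.393 for two-sided 0.0167, SE0 pooled and SE1 unpooled. For pain freedom, d = 0.10, SE0 = √(2 × 0.17 × 0.83/380) = 0.0273 and SE1 = √((0.22 × 0.78 + 0.12 × 0.88)/380) = 0.0270. Power is 0.901. MBS freedom gives 0.903 and the product is 0.814. The stated 90%, 90% and roughly 80% reproduce.

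**Size of the relapse comparison.** 0.22 × 380 = 83.6 and 0.12 × 380 = 45.6, so about 84 v 46 subjects.

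**Assumptions, because the documents give no relapse rates.** 12% of subjects would be pain free on either treatment and relapse at rate rA. A further 10% are pain free only on active and relapse at rate rD. Nobody is pain free only on placebo. Treatment changes no subject's relapse. Strata are ignored because no stratum rates are given. Then expected relapse is (12·rA + 10·rD)/22 on active and rA on placebo.

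**One case in full (rA = 50%, rD = 20%).** Active: (600 + 200)/22 = 36.4%. Placebo: 50%. Difference: 13.6 points. Pooled proportion 0.412; SE0 = √(0.412 × 0.588 × (1/84 + 1/46)) = 0.0903; SE1 = √(0.364 × 0.636/84 + 0.25/46) = 0.0905. Rejection = Φ[(0.136 − 2.393 × 0.0903)/0.0905] = 0.19, nearly all in favour of BHV-3500.

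**Range.** The last two columns come from simulation with 400,000 trials per case and pooled variance. The final column also requires 2-hour pain freedom and sustained pain freedom from 2 to 48 hours to be significant. It is a share of all trials, not of those that pass the two tests.

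| rA | rD | Expected relapse, active v placebo | Favours | Relapse test alone | With the two earlier tests |
|---|---|---|---|---|---|
| 50% | 20% | 36.4% v 50% | BHV-3500 | 19% | 17% |
| 40% | 20% | 30.9% v 40% | BHV-3500 | 9% | 8% |
| 40% | 30% | 35.5% v 40% | BHV-3500 | 3% | 3% |
| 40% | 40% | 40% v 40% | neither | 1.7% | no higher |
| 20% | 50% | 33.6% v 20% | placebo | 21% | 2.3% |
| 20% | 60% | 38.2% v 20% | placebo | 39% | 2.8% |

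With unpooled variance the first three cases give 19.4%, 8.7% and 3.1% in favour of BHV-3500 for the test alone, so the choice of variance matters little there.

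**Why the earlier tests act so differently in the two directions.** Ignoring the rescue and missing-data rules, sustained pain freedom is 12(1 − rA) + 10(1 − rD) percent on active and 12(1 − rA) percent on placebo. At 50% and 20% this is 14% v 6%, which is usually significant (power 0.90). At 20% and 60% it is 13.6% v 9.6%, which usually is not, so testing stops before relapse is reached. Extra relapse among drug-only responders therefore tends to block the test that it would bias.

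**The case against.** A reader might infer that the stated type I error control fails for this endpoint. The documents do not support that. The SAP's estimand is the difference in relapse percentages within the 2-hour pain-free subsets, and the test keeps its nominal level when those percentages are equal. In the cases above the percentages do differ, so rejection is correct for that null. What fails is the causal reading.

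A reader might also take the 21% and 39% as rates of false superiority. They are not. Those rejections favour placebo, and they fall to between 2% and 3% once two of the preceding tests must succeed. The SAP uses the word superiority for the co-primary tests only. For relapse that reading comes from the placebo comparison, the flag and the plot direction.

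The best defence is about reach. All 14 earlier secondary endpoints must be significant first, which lowers every figure in the final column further. Relapse is last, so an error opens no further test. The subset is disclosed, and numerators and denominators are displayed. Protocol 1.3.2 says a selected dose will be retested. The larger false-benefit figures need drug-only responders to relapse much less than the others, and nothing in the documents points in that direction.

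All of this stands as a limit on size. It does not answer the interpretive point, because nothing in the plan supports equal relapse tendency in the two kinds of responder either. A caveat sentence alone would meet much of the concern, but it would sit awkwardly beside a significance flag.

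**Conclusion.** The concern holds as a limit on interpretation. The relapse comparison conditions on a post-dose outcome that treatment changes, so a significant difference, in either direction, cannot be attributed to an effect of BHV-3500 on relapse.

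The size depends on assumed relapse rates. With no true effect on relapse, a result favouring BHV-3500 arises in about 3% to 19% of trials across the cases examined, and in about 3% to 17% after the two earlier tests. Equal rates return the nominal 1.67%. Where drug-only responders relapse more, the bias runs against the drug and could hide a real benefit, though the hierarchy usually stops first. These figures assume no placebo-only responders and the planning rates for pain freedom. The consequence is confined to the relapse claim. The co-primary results and the other secondary tests are unaffected.

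**What to change.** In SAP 1.2.2, 6.1.2, 6.3.4, 6.3.4.9 and 6.3.4.10 and in Protocol 2.2 and 9.4.2, take pain relapse out of the confirmatory hierarchy. SAP 1.2.2 and Protocol 2.2 must be included because they set the test order. Report relapse as descriptive percentages with confidence intervals by treatment group, without a significance flag, and state that it is not a randomised comparison. State also that sustained pain freedom from 2 to 48 hours in all mITT subjects, already secondary endpoint 13, is the comparison of durability without post-dose selection on pain freedom.

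The cost is wording in two documents and the loss of a formal relapse claim, which this design cannot support as a treatment effect. Because relapse is tested last, no other test, alpha level or sample size changes.

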### 6.3.4.10 Overall Summary of Primary and Secondary Endpoints

An overall summary of treatment comparisons of all primary and secondary endpoints tested hierarchically will present the following statistics:

- Overall response rate (i.e., "n/N" and percentage) and 98.3% CI for each treatment group
- Stratified percentage difference between treatment groups (BHV-3500 placebo), 98.3% CI, and p-value.

Analyses will be based on principal methods described in Sections 6.3.3 and 6.3.4. Endpoints will be displayed in the order presented in Sections 1.2.1 and 1.2.2. P-values that are determined to be significant based on the testing hierarchy will be flagged.

A forest plot of treatment comparisons of all primary and secondary endpoints tested hierarchically will be produced for each treatment group comparison of BHV-3500 versus placebo based on the overall summary. Each plot will display the following statistics:

- Overall response rate (i.e., "n/N" and percentage) for the BHV-3500 treatment group and placebo
- Stratified percentage difference between treatment groups (BHV-3500 placebo) and 98.3% CI.

Percentage differences with p-values that are determined to be significant based on the testing hierarchy will be flagged. Note that each plot will display results for *no* intervening rescue medication use within 24 hours post-dose and *no* pain relapse from 2 to 48 hours post-dose so that positive percentage differences will favor BHV-3500 for these secondary endpoints.

# 6.3.5 Exploratory Efficacy Endpoints

All exploratory efficacy endpoints will be evaluated for mITT subjects, unless specified otherwise.

Any p-values presented for exploratory efficacy endpoints are for descriptive purposes only, and not included in the hierarchical testing.

### 6.3.5.1 Return to Normal Function at 24 Hours

Return to normal function outcomes at 24 hours post-dose will be summarized by treatment group (see Section 6.3.5.2).

## 6.3.5.2 Efficacy at Each Post-Dose Time Point

## **Efficacy Outcomes Over Time: Principal Analyses**

Efficacy outcomes will be summarized for mITT subjects by treatment group as the number and percentage of subjects in categories (responder; failure; failure subcategories) at each time point from 15 minutes through 48 hours post-dose. Subjects who are not classified as responders at a time point will be classified as failures. Failure subcategories are mutually exclusive, because subjects who meet more than 1 failure criterion will be classified according to the first failure criterion met; in case of ties, the first failure subcategory that is met in the specified hierarchy for an endpoint will be chosen. Percentages for response rates will also be shown with exact Clopper-Pearson 98.3% CIs.

Outcomes will be presented separately for each of the following efficacy endpoints: pain freedom, MBS freedom, pain relief, nausea freedom, phonophobia freedom, photophobia freedom, and return to normal function. These analyses will use the NC=F and RM=F methods to align with principal analyses of co-primary and secondary endpoints (see Sections 6.3.3.1 and 6.3.3.2). Outcomes category nomenclature is as follows:

- "at time point" means in the analysis window corresponding to that post-dose time point
- "No intervening rescue medication taken at or before time point" means rescue medication start date/time missing or > {eDiary finding date/time in the analysis window corresponding to that post-dose time point}
- "Rescue medication taken at or before time point" means (rescue medication start date/time study drug start date/time) ≤ upper bound of the analysis window corresponding to that post-dose time point (see Section 7.5).

Outcomes for mITT subjects will be presented over time as described below. Subjects who are not included in the mITT population sample will have the following outcomes in by-subject listings:

- Randomized subjects not in the mITT population sample: "Not mITT"
- mITT subjects with absent or missing symptom status at on-study migraine attack onset for nausea freedom, photophobia freedom, and photophobia freedom: "Not evaluable: symptom absent at onset" or "Not evaluable: symptom missing at onset"
- mITT subjects with normal or missing functional disability level at on-study migraine attack onset for return to normal function: "Not evaluable: normal function at onset" or "Not evaluable: missing disability level at onset".

#### **Pain Freedom Outcomes Over Time**

Outcomes categories are defined as:

• Responder: No pain at time point and no intervening rescue medication taken at or before time point

#### Failure

- o Rescue medication taken at or before time point (RM=F)
- o Mild, moderate or severe pain at time point
  - Severe pain
  - Moderate pain
  - Mild pain
- o Missing pain level at time point (NC=F).

### **MBS Freedom Outcomes Over Time**

Outcome categories are:

- Responder: MBS reported at on-study migraine attack onset before taking study drug, MBS absent at time point, and no intervening rescue medication taken at or before time point
- Failure
  - Missing MBS at on-study migraine attack onset
  - o Rescue medication taken at or before time point (RM=F)
  - o Nausea reported as MBS at on-study migraine attack onset and present at time point
  - Phonophobia reported as MBS at on-study migraine attack onset and present at time point
  - Photophobia reported as MBS at on-study migraine attack onset and present at time point
  - o Missing MBS status at time point (NC=F).

### **Pain Relief Outcomes Over Time**

Outcome categories are defined as:

- Responder: Mild or no pain at time point and no intervening rescue medication taken at or before time point
- Failure
  - Rescue medication taken at or before time point (RM=F)
  - o Moderate or severe pain at time point
    - Severe pain
    - Moderate pain
  - o Missing pain level at time point (NC=F).

## Nausea Freedom, Photophobia Freedom and Phonophobia Freedom Outcomes Over Time

Freedom from each symptom (nausea, phonophobia, and photophobia) will be evaluated separately. Analyses will be based on mITT subjects with the symptom present at on-study migraine attack onset (see Section 7.6.3.2).

Outcomes categories are defined as:

- Responder: symptom absent at time point and no intervening rescue medication taken at or before time point
- Failure
  - o Rescue medication taken at or before time point (RM=F)
  - Symptom present at time point
  - Missing symptom status at time point (NC=F).

#### **Return to Normal Function Outcomes Over Time**

Analyses will be based on mITT subjects with functional disability at on-study migraine attack onset.

Outcomes categories are defined as:

- Responder: normal at time point and no intervening rescue medication taken at or before time point
- Failure
  - Rescue medication taken at or before time point (RM=F)
  - Functional disability at time point
    - Requires bedrest
    - Moderately impaired
    - Mildly impaired
  - Missing functional disability level at time point (NC=F).

### **Complete Cases Over Time: Sensitivity Analyses**

Response rates corresponding to efficacy outcomes over time will also be presented using complete cases for each of the following efficacy endpoints: pain freedom, MBS freedom, pain relief, nausea freedom, phonophobia freedom, photophobia freedom, and return to normal function. Percentages for response rates will also be shown with exact Clopper-Pearson 98.3% CIs.

In these sensitivity analyses, subjects who are missing data in a post-dose time point analysis window will be excluded at that time point (NC=M). Results for the co-primary endpoints of

pain freedom and MBS freedom at 2 hours post-dose will be the same as those for the complete cases sensitivity analyses (see Sections 6.3.3.1 and 6.3.3.2).

For MBS freedom, the following conventions will be applied: (1) first, subjects whose MBS at on-study migraine attack onset is missing will be classified as failures; (2) next, the RM=F method of handling intervening rescue medication use will be applied; (3) finally, subjects with missing data in the analysis window will be excluded.

For all other endpoints, the RM=F method of handling intervening rescue medication use will be applied first, and then subjects with missing data in the analysis window will be excluded.

